This demonstration project has the potential to improve short and long term outcome of infants suffering from NAS while decreasing the cost of their care. It aims at doing so by 1) reaching out to qualifying mothers prior to delivery; 2) empowering those mothers during their infant hospital stay by further educating them on NAS and means of comforting and easing their infant's withdrawal symptoms; 3) discharging infants home while still on narcotic treatment under very close medical supervision until complete weaning is achieved; 4) ensuring a safe home environment and healthy maternal involvement throughout withdrawal and for a year after cessation of medical treatment.

Principal Investigator: [name], MPH

Application Number: IRB00107690

2. Objectives

Primary Objective: Compare the LOS of NICU infants with NAS treated with methadone with historical data and a comparison group of NICU NAS infants treated with a different narcotic agent.

Secondary Objectives:

- 1) Compare maternal bonding between methadone treated infants and those treated with a different narcotic,
- 2) Assess if methadone treatment leads to decreased maternal depressive symptomatology as compared to treatment with other narcotics;
- 3) Study whether methadone treatments leads to safer transition to home with no readmissions to the hospital within 30 days for NAS-related reasons;
- 4) Compare proportions of children who gain weight (greater than 15% above birth weight) at 30 days of age between methadone treated and non-treated infants;
- 5) Compare the incidence of providing breast milk (> 50% of nutritional needs) at 30 days of age between methadone treated and non-treated infants;
- 6) Assess the age appropriate infant development at 4, 8 and 12 months of age among the methadone treatment group;
- 7) Determine the response percentage of mothers who are screened as eligible by PAR officials and who agree to participate in the demonstration project;
- 8) Assess the drop out percentage of mothers who agree to participate but do not follow through with home discharge for continued care;
- 9) Quantitate the proportion of mothers who feel comfortable with home care of their infant at discharge;
- 10) Monitor the readiness of mothers to assess infant on 3 to 4 hours intervals while at home;
- 11) Determine the compliance rate with the Johns Hopkins All Children's Hospital (JHACH) pediatrician visits.

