- 2) Major concomitant medical illness including planned antibiotic treatment for greater than 3 days or NPO status;
- 3) Infants who are being placed for adoption;
- 4) Infants in significant pain requiring narcotic medication for comfort (for example those with a fracture);
- 5) Infants whose maternal UDS at the time of delivery is positive for any other drug of abuse beside opiates;
- 6) Mother with hearing or language impairment.

Comparison Group:

Inclusion Criteria:

- 1) Baby is diagnosed with neonatal abstinence syndrome;
- 2) Newborns \geq 37 0/7 weeks gestation;
- 3) Newborns transferred to JHACH within 72 hours from birth;
- 4) Newborns \geq 2.5 kg weight at birth;
- 5) Informed parental consent.

Exclusion Criteria:

- 1) Infant not requiring pharmacologic treatment for NAS;
- 2) Major congenital anomalies;
- 3) Major concomitant medical illness including planned antibiotic treatment for greater than 3 days or NPO status;
- 4) Infants who are being placed for adoption;
- 5) Infants in significant pain requiring narcotic medication for comfort (for example those with a fracture);
- 6) Mother with hearing or language impairment;
- 7) Infants known upon admission who will be placed into state custody or sheltered.

Principal Investigator: [name], MPH

Application Number: IRB00107690

Study Procedures

- a. **Study design, including the sequence and timing of study procedures** (distinguish research procedures from those that are part of routine care).

General Design Issues:

The proposed demonstration project is a non-randomized, un-blinded feasibility study. A prospective cohort study design will be implemented.

Eligibility and Enrollment Process:

a) **Methadone Treatment Group:** Mothers who meet the criteria for enrollment in the demonstration project will be identified by the Operation PAR personnel during the last month of pregnancy. Such individuals will be approached by PAR personnel to determine their willingness to learn more about the methadone study. If they are interested, their contact information will be given to a study team member at Kids Home Care. The Kids Home Care study team member will contact the mother via telephone to discuss the study and may provide mother with a copy of the informed consent in order to give the mother ample time prior to delivery to ask questions of the study team.

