JHACH NICU Stork Nurses communicate with the Bayfront Baby Place Nurses a minimum of two times per day to check for potential NAS infants and transfers. Such communication readily identifies candidate mother / infant dyads shortly after delivery, and the pre-qualified mother will be approached for consent by a member of the study team (MD or mid-level).

b) **Comparison Group:** Mothers of infants who are admitted to the JHACH NICU with the diagnosis of NAS and who are started on treatment with a narcotic different than methadone, will be identified during the first week of NICU admission. Those mothers will be approached for consent by a member of the study team.

The difference between the two groups is further delineated in the tables below.

NOTE regarding screen failures:

Up to 35% of infants with NAS do not require pharmacological treatment as their symptomatology is controlled by non-pharmacological interventions. Such infants are released home after an observation period of about 7 days. If a patient was consented for either the comparison or methadone group and did not require pharmacological treatment for NAS, these infants will be considered screen failures. Accordingly, there will be no measures of bonding and depression, no outpatient follow-up by either KHC or the JHACH pediatrician and no assessment of development.

Principal Investigator: [name], MPH

Application Number: IRB00107690

Study Design:

Study Schedule of Events:

a) Methadone Treatment Group

Study Intervention	Enrollment	While inpatient	After discharge home on methadone	6 – 8 weeks of age	4 months of age	8 months of age	12 months of age
Informed Consent	X						
Methadone Administration		X ^a	X ^b				
Child Protective Investigator (CPI) clearance of the home		X (prior to discharge)					
Social Work Home Assessment			X (upon discharge)				
Face-to-face teleconferencing			X ^c				
Finnegan scoring		X	X ^b				
Kids Home Care Visit			X ^b		X ^f	X ^f	X ^f
JHACH Outpatient Pediatrician H&P, PE			X ^d				
The Postpartum Bonding Questionnaire (PBQ)		X ^e		X ^f			
Edinburgh Postnatal Depression Scale (EPDS)		X ^e		X ^f			
Ages And Stages Questionnaire (ASQ)					X	X	X

^a Per protocol

^b Twice daily until 48 hours after total weaning of medication is achieved

^c Every 3-4 hours until 48 hours after total weaning of medication is achieved

^d Within 1-2 days after discharge then weekly for 4 weeks until discontinuation of methadone treatment

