It is standard of care for infants discharged from the JHACH NICU to see their primary care provider (PCP) within a day or two of discharge. Follow-up will be provided by an IRB approved study team JHACH Pediatrician, and will take place within one or two days after discharge then weekly for 4 weeks after discontinuation of methadone treatment.

G. Off-treatment Criteria:

Principal Investigator: [name], MPH

Application Number: IRB00107690

Off-treatment is defined as an infant who no longer qualifies for discharge home on methadone – i.e. requiring adjuvant pharmacological therapy or re-admission to the hospital while still on methadone

1. Addition of adjuvant therapy:

It is common for infants suffering from NAS to require the addition of an adjunct therapeutic agent for control of symptoms. This second-line agent varies among institutions but consists often of phenobarbital.

If demonstration project participants have uncontrolled NAS symptoms (defined as a 24-hour Finnegan score average ≥ 11 despite comfort measures and maximal methadone dosing – i.e. 0.1 mg/kg given every 4 hours), the infant will be placed on phenobarbital, the standard of care at JHACH NICU. Such infant will be off-treatment from the study i.e. will not qualify for subsequent discharge home prior to discontinuation of methadone. Maternal assessments of bonding and depression will remain ongoing. There will be no home nursing visits.

2. Re-admission to the JHACH NICU:

It is common for infants suffering from NAS not to tolerate weaning off medication. Re-escalation during that phase is common. If during the weaning phase, infant's Finnegan scores are > 8 on 2 consecutive scores despite comfort measures, the dose of methadone will be increased to the previous dose at which the patient's symptoms were well controlled.

If an infant requires consecutive re-escalation of medication with no control of symptoms (i.e. 24 hour Finnegan scores > 6), such infant will be re-admitted to the hospital.

- for infants who were discharged home on a dose of methadone that is < 0.04 mg/kg, such infant will be re-admitted to the hospital if consecutive re-escalation of methadone are required and infant reaches a dose of 0.05 mg/kg.

- for infants discharged home at a dose of 0.04 mg/kg, who do not tolerate weaning at home and who require dose escalation, the dose will be increased in 2 increments per protocol to a value of 0.07 mg/kg before re-admission to the hospital.

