JHACH admitted and average of 131 NAS infants in recent years who required pharmacological treatment for NAS. Approximately 30% of those mother/infant dyads were residents of PAR. We anticipate to enroll 25 mother/baby dyads into the methadone treatment group and 25 mother/baby dyads into the control group for a total of 100 participants. Both the mother and infant are research participants. Those infant participants are defined as 1) needing methadone or other opiate treatment, 2) transitioning to home care, and 3) successfully weaning off medication.

This number has been extrapolated taken into account the following projections/assumptions: 1) not all mothers staying at PAR will meet criteria for participation, and 2) polydrug use may be discovered at the time of delivery thus excluding from participation, and 3) 20-40% of infants enrolled may need adjunct second line therapy.

b. Blinding, including justification for blinding or not blinding the trial, if applicable.

This is a demonstration study with no blinding of subjects involved.

c. Justification of why participants will not receive routine care or will have current therapy stopped.

All infants will continue to receive routine hospital care. Methadone treatment is approved by the FDA, and endorsed by the AAP for inpatient and outpatient treatment of infants with NAS. While methadone is not used as the standard of care at JHACH NICU for infants with NAS at birth, it is still used for later iatrogenic withdrawal in the NICU and other intensive care units in the hospital.

d. Justification for inclusion of a placebo or non-treatment group. N/A Will need to justify this as a comparison groups has been included

e. Definition of treatment failure or participant removal criteria.

As delineated above, infants will be off-treatment from the demonstration project if 1) they require the addition of a second-line of pharmacological treatment or 2) they require re-admission to the

Principal Investigator: [name], MPH

Application Number: IRB00107690

hospital. Data will still be collected until final hospital discharge for these infants and the maternal assessments of bonding and depression will remain ongoing. .

Other Indications for participant off-study:

- a. Parent withdraws informed consent at any time
 - b. Infant transfers to another hospital.
 - c. Infant experiences an unexpected adverse event deemed related to study intervention

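### Secondary objective 9 (mothers' comfort at discharge) has no data source, and objective 7 has no described count of mothers who decline at PAR; objective 8 needs only a reporting definition

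*Combined protocol and SAP*

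**What the plan says.** Under General Design Issues the protocol describes itself as a feasibility study. Three of the eleven secondary objectives in section 2 concern uptake of home methadone.

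- **Objective 7:** "Determine the response percentage of mothers who are screened as eligible by PAR officials and who agree to participate in the demonstration project". Under Eligibility and Enrollment Process, PAR personnel identify and first approach these mothers. Then: "If they are interested, their contact information will be given to a study team member at Kids Home Care". After delivery, "the pre-qualified mother will be approached for consent by a member of the study team".
- **Objective 8:** "Assess the drop out percentage of mothers who agree to participate but do not follow through with home discharge for continued care". Elsewhere the protocol names other exits. Consented infants who need no drug treatment are screen failures (NOTE regarding screen failures). Infants given adjunct therapy are off-treatment and "will not qualify for subsequent discharge home prior to discontinuation of methadone" (Off-treatment Criteria). Under Accrual, the expectation is that "20-40% of infants enrolled may need adjunct second line therapy". Clearance of the home by a Child Protective Investigator is also required before discharge.
- **Objective 9:** "Quantitate the proportion of mothers who feel comfortable with home care of their infant at discharge".

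Section 6 lists one primary and five additional outcomes: bonding, depressive symptoms, 30-day readmission, weight gain and development. None corresponds to objectives 7, 8 or 9.

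**The concern.** A feasibility percentage needs a defined denominator, a rule for the numerator and a place where the data are recorded. Objective 9 has no place of recording. Objective 7 names its denominator, but part of that denominator is filtered out before the study team meets anyone, and no record of it is described. Objective 8 has wording but no counting rule.

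The protocol states that there are no published data on in-home drug treatment of these infants. A reader judging whether the model is workable will therefore want to know how many eligible mothers accepted it, how many withdrew, and how many felt able to manage at home. A refusal that nobody logged and a question that nobody asked cannot be reliably recovered at the analysis stage.

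**Working it through.** **The plan's own figure.** Objectives 7 to 9 carry no sample size, precision or target. The only power statement is for length of stay: difference 4 days, SD 5, alpha 0.05, 80% power, 25 per group. Two-sided, n = 2 × (1.96 + 0.84)² × 5² / 4² ≈ 24.5, rounded up to 25. Power at 25 per group is 80.7% by the normal approximation and 79.1% by the t-test. The figure reproduces, and nothing below alters it.

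**Objective 9: search for a source.**

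| Place | Content relevant to comfort with home care |
|---|---|
| Schedule of Events, methadone group | PBQ, EPDS, ASQ, visits and scoring; no comfort item |
| Schedule of Events, comparison group | PBQ and EPDS only |
| Questionnaire sections | PBQ and EPDS safety plans and ASQ; no comfort item |
| Section 6 | Outcome not listed; no analysis |

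The nearest measure is the third PBQ component, which covers anxiety about the baby and about caring for it. In the PBQ safety plan its cut-off (above 9) flags a bonding concern and triggers counselling. The inpatient PBQ is given during weaning, which need not be at discharge. No passage links it to objective 9.

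**Objective 7: what the filter can do.** There are three points at which a mother can decline: to PAR staff, in the Kids Home Care telephone call, and at consent after delivery. The study team sees the last two. Let d be the share of eligible mothers declining at PAR and c the share of referred mothers declining later.

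- Response over eligible mothers = (1 − d)(1 − c)
- Response over referred mothers = 1 − c

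The documents give neither d nor c, so these are assumed ranges: d = 20-60%, c = 0-20%.

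| d | c | Over eligible | Over referred |
|---|---|---|---|
| 20% | 0% | 80% | 100% |
| 20% | 20% | 64% | 80% |
| 40% | 10% | 54% | 90% |
| 60% | 0% | 40% | 100% |
| 60% | 20% | 32% | 80% |

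The gap depends on d alone as a ratio: the rate over referred mothers is 1/(1 − d) times the rate over eligible mothers, that is 1.25 to 2.5 times here.

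**Objective 8: how far the reading can move.** Take 25 treated dyads, and assume that the 20-40% adjunct share applies to treated infants and that the need arises before discharge.

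- 25 × 0.20 = 5 and 25 × 0.40 = 10 infants could not go home on methadone, whatever the mother wished.
- If they were lumped into drop-out with no mother leaving: 5/25 = 20% (exact 95% interval 6.8-40.7%) to 10/25 = 40% (21.1-61.3%).
- If they are kept apart and no mother leaves: 0/25 = 0% (0-13.7%).
- If 10% of those able to go home also dropped out, the lumped figure would be 0.20 + 0.80 × 0.10 = 28% to 0.40 + 0.60 × 0.10 = 46%.

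Accrual also describes the counted infants as having moved to home care and completed weaning. Used as a denominator, that description would remove every drop-out by construction.

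**The case against.** The strongest reply is that the documents are silent on these points rather than wrong. Objective 7 already states the correct denominator. PAR does the screening and has agreed to help identify participants, and the sentence on contact details governs the transfer of personal data without ruling out an aggregate count. That is fair. The acceptance rate would be too high only if the study fell back on the mothers it sees. What stands is that no route for obtaining the stated denominator is described.

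A reader might infer that mothers who decline never reach the study at all. The documents do not support this, because refusals by telephone or at consent after delivery are made to the study team. Only refusals at PAR are unrecorded.

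A reader might also infer that objective 8 counts mothers whose infants could not go home on methadone. The documents do not support this either. The objective's subject is the mother's conduct, screen failure and off-treatment are separately named categories, and no passage places either group in the drop-out percentage. In particular, nothing justifies adding the group described by "Up to 35% of infants with NAS do not require pharmacological treatment as their symptomatology is controlled by non-pharmacological interventions" to drop-out, since those infants leave the study assessments as screen failures. What stands is a missing definition.

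On objective 9, PBQ factor 3 might be offered as a proxy. It could inform the question, but the plan does not assign it that role, and a cut-off for bonding concern does not define comfort with home care.

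Finally, these are three of eleven secondary objectives, and none is in the section 6 outcome list. That bears on priority. It does not supply the missing data.

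**Conclusion.** The point holds for objective 9 without qualification: following the plan produces no data on comfort at discharge. It holds in a limited form for objective 7: the denominator is named, but no count of mothers who decline at PAR is described. Under the assumed refusal ranges, a rate computed over referred mothers would read 80-100% against a true 32-80%. Those figures illustrate the possible size and do not predict it.

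For objective 8 the conclusion is only that a counting rule should be written. The most that lumping off-treatment infants into drop-out could do is produce 20-40% of treated dyads with no mother leaving. This rests on the protocol's own adjunct range applied to 25 treated dyads. It would not be right to say that all three objectives are unanswerable: 7 and 8 can be answered once a source and a definition are stated.

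The length-of-stay comparison, its sample size and the safety stopping rules are unaffected. The change is worth making because it is cheap before enrolment and much of the missing information cannot be recovered afterwards.

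**What to change.** 1. **Objective 9.** Add one fixed-response question on comfort with home care for methadone-group mothers, asked at discharge or at the last contact before it. The inpatient PBQ/EPDS contact serves only if it is that last contact. State which responses count as comfortable and who forms the denominator, and list the item in the schedule of events and in section 6.
2. **Objective 7.** Ask PAR for a de-identified aggregate count of mothers found eligible, approached, interested and declined. State at which step a mother is taken to have agreed, and compute the percentage over eligible mothers. Report later refusals, by telephone and at consent, as further steps in the same flow.
3. **Objective 8, as a reporting clarification.** Among consented, treated dyads, tabulate every reason for no home discharge on methadone. Use separate rows for maternal withdrawal or refusal (including before the infant is stable), off-treatment before discharge, home-clearance failure, and other reasons such as transfer. Report screen failures apart. Do not restrict the denominator to dyads that met the discharge stability criteria, because that would lose mothers who withdraw earlier. Do not merge home-clearance decisions with maternal choice. Give exact 95% intervals.

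The cost is one extra question, minor recording by PAR personnel, one flow table and a few lines in section 6. The reported acceptance rate may be lower than one based on referred mothers.

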Protocol Title: Methadone Demonstration Project

NCT03134703

Protocol v5: 02.02.2018

JHM IRB - eForm A – Protocol

- **Use the section headings to write the JHM IRB eForm A, inserting the appropriate material in each. If a section is not applicable, leave heading in and insert N/A.**
- **When submitting JHM IRB eForm A (new or revised), enter the date submitted to the field at the top of JHM IRB eForm A.**

1. Abstract

- a. Provide no more than a one page research abstract briefly stating the problem, the research hypothesis, and the importance of the research.

The Problem:

Infants who are born to mothers taking or abusing opiates frequently suffer from neonatal abstinence syndrome (NAS) after birth. They often have withdrawal symptoms which can be life-threatening if untreated. The American Academy of Pediatrics (AAP) recommends non-pharmacologic treatment as first-line therapy, followed by opioid replacement for severe cases. The pharmacologic treatment usually takes place within the hospital setting. Such approach often incurs prolonged hospitalization and significant financial burden. It also creates barriers to adequate maternal/infant bonding with potential deleterious consequences for the infant's long term emotional and societal outcomes.

The Research Hypothesis: Among Neonatal Intensive Care Unit (NICU) infants diagnosed with NAS and requiring pharmacological treatment, those who are treated with methadone will have a shorter Length of Stay (LOS) of less than 15 days as compared to the average length LOS of 25 days of NAS infants admitted in recent years at Johns Hopkins All Children's Hospital (JHACH) NICU.

The Importance of the Research:

Infants suffering from NAS are historically cared for in the hospital setting and are not discharged home until all narcotic medications have been weaned off. Such prolonged hospital stay invariably equates to prolonged separation of mother and baby. Consequently, infants suffer from the absence of a care giver who could provide constant comforting techniques which are the mainstay of treatment of infants with NAS. This in turn leads to further prolongation of the hospital stay and impaired mother-infant bonding.

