Research illustrates that early bonding between parent/caregiver leads to improved outcomes of the infant suffering from NAS. This demonstration projects allows for a greater participation of the mother in the care of her infant while inpatient. It will also empower her to better understand the nature of neonatal drug withdrawal, to recognize its signs in a timely fashion and to provide better non-pharmacological care for her infant with proven comfort and feeding techniques.

The project will also provide home support and close monitoring as well as regular developmental follow-up for these infants through our JHACH NICU follow-up clinic, hence identifying and quickly responding to delays. These infants are prone to have developmental issues and recent research is demonstrating they have problems upon entering the school systems at age 4 and 5 years. While we have follow-up clinics in St Petersburg and Sarasota, the current Medicaid system and Medicaid HMO's are not funding these infants to come to the clinics, as they are considering it primary care. JHACH NICU follow-up clinic is much different than primary care, is multidisciplinary and offers standardized psychometric testing and referrals for services as deemed indicated.

4. Inclusion/Exclusion Criteria for Mother/Baby dyad

Methadone Treatment Group:

Inclusion criteria

- 1) Baby is diagnosed with neonatal abstinence syndrome;
- 2) Mother under the care of Operation PAR;
- 3) Mother resides in Pinellas or Pasco county at the time of enrollment and is expected to throughout the infant's methadone treatment period;
- 4) Mother has been deemed by PAR officials as being compliant with the detoxification program;
- 5) Mother has completed induction methadone treatment and has had no changes in medication dosage of 10% or greater in the two weeks preceding delivery;
- 6) Mother has been prescreened and deemed adequate candidate by the demonstration project team members;
- 7) No known concerns from Florida Department of Children and Families (DCF) regarding the infant's ability to return to the home;
- 8) Newborns ≥ 37 0/7 weeks gestation;
- 9) Newborns transferred to JHACH within 72 hours from birth;
- 10) Newborns ≥ 2.5 kg weight at birth; Informed parental consent.

Principal Investigator: [name], MPH

Application Number: IRB00107690

Exclusion Criteria

- 1) Major congenital anomalies;

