- a. **Primary outcome variable:** Length of Stay (LOS)

- b. **Additional outcomes of interest to be examined:**

- 1) Maternal bonding measured by the Postpartum Bonding Questionnaire (PBQ);
- 2) Depressive symptomatology measured by Edinburgh Postnatal Depression Scale (EPDS);
- 3) Hospital readmission within 30 days;
- 4) Weight gain of greater than 15% above Birth Weight at 30 days of age;
- 5) Age appropriate development as screened by the Ages and Stages questionnaires.

- c. **Statistical plan including sample size justification and interim data analysis:**

Demographic and clinical characteristics of participants will be summarized using means with standard deviations (SD) or median with interquartile ranges for continuous variables and counts and percentages for categorical variables. The primary outcome, length of stay, will be summarized using mean (SD) or median and interquartile range and will be compared to the comparison group using the t-test or Wilcoxon rank sum test as appropriate. For the secondary outcomes, the scores on the postpartum bonding questionnaire or the Edinburgh Postnatal Depression Scale will be summarized using means (SD) and compared to other patients in the comparison group using independent two-sample t-test. The proportion of participants that are readmitted within 30 days or with a weight gain of greater than 15% above birth weight will be compared to the comparison group using a Chi-squared or Fishers exact test as appropriate. Among the methadone cohort, we will calculate percentage of infants with age appropriate development at 4, 8 and 12 months. We anticipate that 25 mother-child dyads in each group will be available for the study. We expect that the mean LOS in the comparison group will be around 25 days (based on historical data). This sample size will allow us to estimate differences in LOS of >4 days with sufficient power (80%) at an alpha of 0.05, assuming a standard deviation of 5 days for both groups.

Early stopping rules:

Infant: requiring therapy with a second drug

Parents: desire to remove the infant from the study at any time or when infant is transferred to another hospital.

7. Risks

- a. **Medical risks, listing all procedures, their major and minor risks and expected frequency:**

Principal Investigator: [name], MPH

Application Number: IRB00107690

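### Only the methadone group has a county-of-residence criterion, so residence may differ between the groups and could bias the unadjusted LOS and bonding comparisons

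*Combined protocol and SAP*

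**What the plan says.** Section 4 (Inclusion/Exclusion Criteria), methadone-group inclusion 3: "Mother resides in Pinellas or Pasco county at the time of enrollment". The same item adds that she should be expected to stay there while the infant is on methadone.

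The comparison group has five inclusion and seven exclusion criteria in the same section, and none concerns residence. The only one related to location is "Newborns transferred to JHACH within 72 hours from birth", which the methadone group must also meet. Eligibility and Enrollment Process, item b, draws comparison dyads from this source: "Mothers of infants who are admitted to the JHACH NICU with the diagnosis of NAS and who are started on treatment" with a narcotic other than methadone. It sets no geographic limit.

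General Design Issues describes a non-randomized, un-blinded cohort. Under Section 6.c, LOS "will be compared to the comparison group using the t-test or Wilcoxon rank sum test as appropriate". PBQ and EPDS scores are compared by an independent two-sample t-test. The section mentions no matching, restriction or covariate.

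On mechanism, the Abstract (The Importance of the Research) says that "infants suffer from the absence of a care giver who could provide constant comforting techniques", and then: "This in turn leads to further prolongation of the hospital stay and impaired mother-infant bonding".

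**The concern.** In a non-randomized comparison, an eligibility rule that binds one group only can make the groups differ before treatment starts. Here the rule concerns where the mother lives. A mother living far from the NICU may be at the bedside less often, whichever narcotic her infant receives. The protocol holds that caregiver absence lengthens the stay and impairs bonding, and both are study outcomes.

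If the comparison group included more distant mothers, its mean LOS could be longer for that reason alone. The unadjusted test would attribute the excess to methadone, and bonding scores could shift the same way. As written, the analysis would neither detect nor correct such an imbalance.

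**Working it through.** **1. The plan's own figure (Section 6.c).** Inputs: 25 dyads per group, SD 5 days, difference 4 days, alpha 0.05, power 80%. Sidedness is not stated; two-sided is taken.

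- n per group = 2 × SD² × (1.960 + 0.842)² / difference² = 2 × 25 × 7.85 / 16 = 24.5, so 25.
- SE of the difference = 5 × √(2/25) = 1.414 days. Power at 4 days is 80.7% (normal approximation) or 79.1% (noncentral t, 48 df).

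The sample-size statement reproduces and is not in question.

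**2. The asymmetry.**

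| | Methadone group | Comparison group |
|---|---|---|
| Mother's residence | Pinellas or Pasco county, at enrollment and through methadone treatment | no criterion |
| Transfer to JHACH within 72 hours of birth | required | required |
| Adjustment for residence in Section 6.c | none | none |

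The transfer rule limits when the infant arrives. It does not limit where the mother lives.

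**3. Size, under assumed inputs.** Let p be the share of comparison mothers living outside the two counties and m the extra days their infants stay. The documents give neither. Then bias = p × m. The false-positive rate is the rejection probability of the two-sided t-test with no true effect (noncentral t, 25 per group, SD held at 5).

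| p | m (days) | Bias (days) | Share of 4 days | Share of 10 days | False-positive rate |
|---|---|---|---|---|---|
| 0 | any | 0 | 0% | 0% | 5.0% |
| 20% | 2 | 0.4 | 10% | 4% | 5.9% |
| 20% | 5 | 1.0 | 25% | 10% | 10.7% |
| 40% | 5 | 2.0 | 50% | 20% | 28.3% |

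Four days is the difference that Section 6.c says can be detected with 80% power. Ten days follows from the hypothesis in the Abstract: under 15 days against an average of 25, and 25 − 15 = 10. The last row puts both assumptions at the top of their ranges.

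**4. Comparison pool (Accrual).** About 131 drug-treated NAS infants were admitted on average in recent years (read here as per year), and about 30% of those dyads were PAR residents. That leaves 131 × 0.70 ≈ 92 others for 25 places. If 20-40% lived outside the two counties, 91.7 × 0.8 ≈ 73 to 91.7 × 0.6 ≈ 55 would remain. All these counts are before the gestation, weight, illness, custody and consent filters.

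**5. Precision of a restricted analysis.** Suppose 25 comparison dyads were already enrolled and the out-of-county ones were set aside.

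- p = 20% leaves 20: SE = 5 × √(1/25 + 1/20) = 1.50 days; power for 4 days 76% (normal approximation).
- p = 40% leaves 15: SE = 5 × √(1/25 + 1/15) = 1.63 days; power for 4 days 69%.
- A 10-day difference is 10 / 1.63 = 6.1 standard errors even in the smaller case, so it would still be detected.

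**The case against.** The case on the other side is substantial, and much of it stands.

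- **The protocol does not link distance to LOS.** A reader might infer from the Abstract that it does. It speaks of caregiver absence and attributes separation to the hospital stay itself. No section connects travel or county with presence or stay. The steps from county to distance to absence are inference, and two whole counties are a rough proxy for distance.
- **No difference in residence is shown.** A reader might also infer that comparison mothers do live farther away, because Section 3 mentions an affiliate hospital and a follow-up clinic in Sarasota. The hospital is mentioned for a discontinued home-methadone practice and the clinic for follow-up after discharge. Neither is named as a source of NAS admissions. The only delivery site named for identifying NAS infants and transfers is Bayfront Baby Place, in the methadone-group enrollment text.
- **Bedside presence differs by design.** Study Procedures, Methadone Treatment group, item A.d, facilitates the mother's presence in the methadone group only. Part of any gap in presence is therefore intervention, not confounding by residence.
- **The rule has a practical reason.** Methadone infants go home on drug with twice-daily nurse visits; comparison infants need no such service.
- **Other differences are more direct.** PAR care and compliance, stable maternal dose, team prescreening and the maternal drug-screen exclusion also apply to the methadone group only, and its infants can be discharged while still on drug.

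The asymmetry survives these points. A practical reason for the rule in one group does not make the groups comparable, and larger threats do not remove a smaller one. Residence precedes treatment, so it can be aligned without touching the intervention.

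**Conclusion.** The criteria allow residence to differ between the groups, and the planned analysis has no means of handling it. It may differ and could bias LOS and bonding; the documents do not support saying that it does. The likely direction favours methadone, provided that mothers living farther away are at the bedside less.

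The size is unknown. The 0.4 to 2.0 days rests entirely on assumed values of p and m. The true bias could be zero if comparison mothers are local. The upper figure, and the false-positive rate of about 28% that goes with it, should be read as an illustration and not as an estimate.

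This is a modest point with a cheap remedy. Correcting it would not by itself make the groups comparable, because the other methadone-only selection rules would remain.

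**What to change.** 1. **Eligibility.** For comparison dyads still to be enrolled, add to the Section 4 comparison-group inclusion criteria that the mother lives in Pinellas or Pasco county at enrollment.
2. **Data.** Record county of residence from the chart for every dyad in both groups.
3. **Analysis.** In Section 6.c, add a sensitivity analysis that repeats the LOS, PBQ and EPDS comparisons in two-county residents only. If every comparison mother proves to be local, report that and close the point.
4. **Maternal visiting.** Do not adjust for it. It is partly intervention, and adjustment would remove some of the effect under study.

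The cost is one line of eligibility text, one chart variable and one extra table. The downsides are a comparison pool smaller than the roughly 92 non-PAR treated dyads, which is itself a count before the other eligibility and consent filters, and lower precision in the restricted analysis. Replacing out-of-county dyads prospectively keeps 25 per group and the planned power. No treatment or clinical procedure changes.
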